7.8.3.1. Hematology

For **WBC differential counts** [total neutrophil (including bands), lymphocyte, monocyte, eosinophil, and basophil counts], the absolute value will be used when reported. When only percentages are available (relevant primarily for neutrophils and lymphocytes, because the CTCAE grading is based on the absolute counts), the absolute value is derived as follows:

$$\text{Derived differential absolute count} = (\text{WBC count}) \times (\text{Differential \%value}/100)$$

If the range for the differential absolute count is not available (ie, the range is only available for the percentage) then Grade 1 will be attributed as follows:

- Lymphocyte count decreased:
 - Derived absolute count does not meet Grade 2-4 criteria, and
 - % value <% LLN value, and
 - Derived absolute count $\geq 800/\text{mm}^3$

- Neutrophil count decreased:
 - Derived absolute count does not meet Grade 2-4 criteria, and
 - % value < % LLN value, and
 - Derived absolute count $\geq 1,500/\text{mm}^3$

7.8.3.2. Chemistry

Liver function tests: Alanine aminotransferase (ALT), aspartate aminotransferase (AST), alkaline phosphatase (ALP), and total bilirubin are used to assess possible drug-induced liver toxicity. The ratios of test result to ULN will be calculated and categorized for these parameters during the on-treatment period.

The summary of liver function tests will include the following categories. The frequency of subjects with each of the following during the on-treatment period will be summarized by treatment arm:

- ALT $>3\times\text{ULN}$, ALT $>5\times\text{ULN}$, ALT $>10\times\text{ULN}$, ALT $>20\times\text{ULN}$
- AST $>3\times\text{ULN}$, AST $>5\times\text{ULN}$, AST $>10\times\text{ULN}$, AST $>20\times\text{ULN}$
- (ALT or AST) $>3\times\text{ULN}$, (ALT or AST) $>5\times\text{ULN}$, (ALT or AST) $>10\times\text{ULN}$, (ALT or AST) $>20\times\text{ULN}$
- Total bilirubin $>2\times\text{ULN}$
- Concurrent ALT $>3\times\text{ULN}$ and total bilirubin $>2\times\text{ULN}$
- Concurrent AST $>3\times\text{ULN}$ and total bilirubin $>2\times\text{ULN}$
- Concurrent (ALT or AST) $>3\times\text{ULN}$ and total bilirubin $>2\times\text{ULN}$
- Concurrent (ALT or AST) $>3\times\text{ULN}$ and total bilirubin $>2\times\text{ULN}$ and ALP $\geq 2\times\text{ULN}$
- Concurrent (ALT or AST) $>3\times\text{ULN}$ and total bilirubin $>2\times\text{ULN}$ and (ALP $<2\times\text{ULN}$ or missing)

Concurrent measurements are those occurring on the same date.

Categories will be cumulative, ie, a subject with an AST $>10\times\text{ULN}$ will also appear in the categories $>5\times\text{ULN}$ and $>3\times\text{ULN}$. Liver function test elevation and possible Hy's Law cases will be summarized using frequency counts and percentages.

An evaluation of Drug-Induced Serious Hepatotoxicity (eDISH) plot will be created, with different symbols for different treatment arms, by graphically displaying:

- Peak serum ALT (/ULN) vs peak total bilirubin (/ULN) including reference lines at ALT = $3\times\text{ULN}$ and total bilirubin = $2\times\text{ULN}$
- Peak serum AST (/ULN) vs peak total bilirubin (/ULN) including reference lines at AST = $3\times\text{ULN}$ and total bilirubin = $2\times\text{ULN}$

In addition, a listing of all total bilirubin, ALT, AST, and ALP values for subjects with a postbaseline total bilirubin $>2\times\text{ULN}$, ALT $>3\times\text{ULN}$, or AST $>3\times\text{ULN}$ will be provided.

For **calcium**, CTCAE grading is based on corrected calcium and ionized calcium. Corrected Calcium is calculated from albumin and calcium as follows:

$$\text{Corrected calcium (mmol/L)} = \text{measured total calcium (mmol/L)} + 0.02 \times [40 - \text{serum albumin (g/L)}]$$

7.8.3.3. Pregnancy Tests

Pregnancy test results will be presented in a by-subject listing.

7.8.4. Vital Signs and Physical Measurements

For all physical measurements and vital sign assessments (height, weight, BMI, BSA, systolic blood pressure, diastolic blood pressure, pulse rate, respiratory rate, temperature) the actual values and the changes from baseline will be summarized by study visit. Change from baseline does not apply to height.

Vital signs and physical measurements will be presented in a by-subject listing.

7.8.5. Electrocardiograms

ECG summaries will include all ECG assessments from the on-treatment period. QTcB and QTcF interval will be derived based on RR and QT interval (see below), if not collected in the eCRF.

Selecting Primary QT Interval Correction for Heart Rate

The analysis of QT interval data is complicated by the fact that the QT interval is highly correlated with heart rate. Because of this correlation, formulas are routinely used to obtain a corrected QT interval, denoted QTc, which is independent of heart rate. This QTc is intended to represent the QT interval at a standardized heart rate. Several correction formulas have been proposed in the literature. For this analysis several of those methods of correction will be used, as described below. The QT interval corrected for heart rate by Bazett's formula, QTcB, is defined as

$$QTcB = \frac{QT}{\sqrt{RR}}$$

and the QT interval corrected for heart rate by the Fridericia's formula, QTcF, is defined as

$$QTcF = \frac{QT}{\sqrt[3]{RR}}$$

where RR represents the RR interval of the ECG, in seconds.

Although Bazett's correction is the historical standard, it does not perform well when heart rate fluctuates. Fridericia's formula may perform better under these conditions. If QTcB and QTcF do not adequately correct for heart rate and there are a sufficient number of subjects (>30) with baseline ECGs, an alternative correction (QTcP) to achieve the goal of getting uncorrelated QTc and RR is based on a linear regression method which yields, theoretically, uncorrelated QTc and RR.

Linear regression method:

- Fit a model $QT (ms)=a+b \times RR (sec)$ to baseline data
- Use the estimated slope, \hat{b} , to correct QT
- Corrected QT for heart rate will be derived as follows:

$$QTcP (ms)=QT (ms)+\hat{b} \times [1-RR(sec)]$$

Data will be summarized using QTcF and QTcB. However, if these are not appropriate for the data set because of an observed large correlation between corrected QT and heart rate using the baseline assessments, the results will also be summarized using QTcP.

ECG Summaries

The following analyses will be performed for each applicable ECG parameter (RR, QT, and QTc) during the on-treatment period. The denominator used to calculate percentages for each category is the number of subjects evaluable for the category.

- Pearson correlation between QT and RR interval, QTc (QTcB, QTcF, and, if applicable, QTcP) and RR interval using baseline assessments
- Frequency of subjects with notable ECG values, defined as those in the following categories:
 - QT/QTc interval increase from baseline >30 ms, >60 ms
 - QT/QTc interval >450 ms, >480 ms, >500 ms

All ECG assessments and qualitative ECG abnormalities will be presented in by-subject listings.

7.8.6. Left Ventricular Ejection Fraction

The LVEF data will be presented in a by-subject listing.

7.8.7. ECOG Performance Status

The ECOG PS shift from baseline to highest score during the on-treatment period will be summarized.

ECOG PS will be presented in a by-subject listing.

7.8.8. Safety Measures Indicative of Clinical Benefit

Transfusion requirements (platelet and RBC; number of units), days spent hospitalized, and other safety measures that are potentially indicative of clinical benefit will be summarized by treatment arm using descriptive statistics.

7.8.8.1.1. On-treatment Transfusions

On-treatment transfusions are defined as transfusions that are started during the on-treatment period.

The summary of on-treatment transfusion data will include the frequency of subjects with any on-treatment transfusions, the frequency of subjects with each type of on-treatment

transfusion (whole blood, packed RBCs, platelet, plasma, and other), the total number of units per subject with each type of on-treatment transfusion, and the reasons for which each type of transfusion is administered.

Transfusion type, number of units, reasons for transfusion administration, and dates of transfusions will be presented in a by-subject listing.

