6.1.2. Secondary Objectives

The key secondary objectives of the study are:

- To compare the complete remission (CR) rate between AG-120 + azacitidine and placebo + azacitidine.
- To compare OS between AG-120 + azacitidine and placebo + azacitidine.
- To compare the CR + CRh rate between AG-120 + azacitidine and placebo + azacitidine; CRh will be derived by the Sponsor.
- To compare the ORR between AG-120 + azacitidine and placebo + azacitidine.

Additional secondary objectives are:

- To compare the CR + CR with incomplete hematologic recovery (CRi) (including CR with incomplete platelet recovery [CRp]) rate between AG-120 + azacitidine and placebo + azacitidine.
- To compare duration of CR (DOCR), duration of CR + CRh (DOCRh), duration of response (DOR), and duration of CR + CRi (including CRp) (DOCRi) between AG-120 + azacitidine and placebo + azacitidine.
- To compare time to CR (TTCR), time to CR + CRh (TTCRh), time to first response (TTR), and time to CR + CRi (including CRp) (TTCRi) between AG-120 + azacitidine and placebo + azacitidine.
- To assess the safety and tolerability of treatment with AG-120 + azacitidine compared with placebo + azacitidine.
- To compare transfusion requirements (platelet and red blood cell [RBC]; number of units transfused), infection rates, days spent hospitalized, and other efficacy and safety measures that are potentially indicative of clinical benefit between AG-120 + azacitidine and placebo + azacitidine.
- To assess the impact of treatment on quality of life (QoL) using the European Organisation for Research and Treatment of Cancer (EORTC) QLQ-C30 and EQ-5D-5L.
- To evaluate the PK of AG-120 as administered in combination with azacitidine.
- To evaluate the PK/PD relationship of AG-120 and 2-HG in blood samples in comparison with placebo.

- To compare rates of CR with IDH1 mutation clearance (MC) between AG-120 + azacitidine and placebo + azacitidine.

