- Subjects should continue to receive therapy with AG-120 or placebo+azacitidine until death, disease relapse, disease progression, development of unacceptable toxicity (AE), confirmed pregnancy, withdrawal by subject, protocol violation, or End of Study.
 - Disease progression (defined only for subjects who have previously attained PR or SD) is defined as evidence for an increase in bone marrow blast percentage and/or increase of absolute blast counts in the blood: 1) >50% increase in bone marrow blast count over baseline (a minimum 15% point increase is required in cases with <30% blasts at baseline); or persistent marrow blast percentage of >70% over at least 3 months; without at least a 100% improvement in ANC to an absolute level (>500/μL, and/or platelet count to >50,000/μL non-transfused); 2) >50% increase in peripheral blasts (white blood cells [WBCs] × % blasts) to >25,000/μL in the absence of treatment-related differentiation syndrome; or 3) new extramedullary disease
 - Subjects with a response less than CR at 24 weeks or beyond can continue on treatment if demonstrating treatment benefit, defined as any of the following: 1) transfusion-independence while on study treatment; 2) ANC >500/μL; or 3) platelets >50,000/μL

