6.3.5. On-Treatment Period

The on-treatment period starts on the date of the start of study treatment and ends 28 days after the end of study treatment.

Data listings will include all assessments and events, with those that occur outside of the on-treatment period flagged.

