7.8.1. Adverse Events

Treatment-emergent adverse events (TEAEs) are AEs with a first onset date during the on-treatment period or worsening from baseline. All summaries described below will be based on TEAEs, if not otherwise specified.

All AEs will be listed by subject and AEs with onset outside of the on-treatment period will be flagged in the listings. Unless otherwise specified, TEAEs will be summarized according

to the latest version of MedDRA by SOC and/or PT, severity (based on CTCAE v4.03 grading), seriousness, and relation to study treatment in decreasing frequency based on the frequencies observed for the AG-120+azacitidine arm.

Each subject will be counted only once within each SOC or PT. If a subject experiences multiple TEAEs under the same PT within a SOC for the same summary period, only the TEAE assessed as related or with the worst severity, as applicable, will be included in the summaries of relationship and severity. If a subject has TEAEs with missing and non-missing grades, the maximum of the non-missing grades will be displayed. No imputation of missing grades will be performed.

The following will be summarized:

- TEAEs by SOC and PT
- TEAEs by SOC, PT, and worst grade
- Most common TEAEs and Grade ≥ 3 TEAEs by PT; these will include TEAEs (any grade) reported in $\geq 10\%$ of subjects in either treatment arm or Grade ≥ 3 TEAEs reported in $\geq 5\%$ of subjects in either treatment arm. These thresholds may be changed based on the observed data without an amendment to this SAP.
- Treatment-related TEAEs, by SOC and PT
- Treatment-related TEAEs, by SOC, PT, and worst grade
- Grade ≥ 3 TEAEs, by SOC and PT
- Treatment-related Grade ≥ 3 TEAEs, by SOC and PT
- Serious TEAEs, by SOC and PT
- Treatment-related Serious TEAEs, by SOC and PT
- TEAEs leading to discontinuation of study drug, by SOC and PT
- TEAEs leading to interruption of study drug, by SOC and PT
- TEAEs leading to dose reduction, by SOC and PT
- TEAEs leading to death, by SOC and PT
- Treatment-related TEAEs leading to death, by SOC and PT

Treatment-related TEAEs (including TEAEs, Grade ≥ 3 TEAEs, serious TEAEs, and TEAEs leading to death) will be summarized separately for

- TEAEs related to AG-120/matched placebo only
- TEAEs related to azacitidine only
- TEAEs related to both AG-120/matched placebo and azacitidine

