7.8.1.1. Adverse Events of Special Interest

The following are considered AESIs:

- QT prolongation (see “AG-120-specified Safety Search Criteria” for the criteria used to identify the relevant AEs)
- Leukocytosis (see “AG-120-specified Safety Search Criteria” for the criteria used to identify the relevant AEs)
- IDH differentiation syndrome (see “AG-120-specified Safety Search Criteria” for the criteria used to identify the relevant AEs)

Additional TEAEs of interest indicative of clinical benefit are as follows (see “AG-120-specified Safety Search Criteria” for the criteria used to identify the relevant AEs):

- Infection
- Bleeding

The following will be summarized for each AESI category and additional TEAEs of interest:

- AESIs/TEAEs of interest by PT
- AESIs/TEAEs of interest by PT and worst grade
- Grade ≥ 3 AESIs/TEAEs of interest by PT
- AESIs/TEAEs of interest leading to discontinuation of study drug by PT
- Serious AESIs/TEAEs of interest by PT
- AESIs/TEAEs of interest leading to death by PT

AESIs/TEAEs of interest leading to discontinuation of study drug will be summarized separately for:

- AG-120/matched placebo only
- Azacitidine only
- Both AG-120/matched placebo and azacitidine

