7.8.8.1.2. Hospitalizations for Adverse Event

Hospitalizations for AE will be summarized, including number of events, total number of days hospitalized, the rate of events and days hospitalized per person-year.

Hospitalizations will be provided in a by-subject listing.

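### Transfusion, infection and bleeding summaries have no time base, so the comparison between arms mixes event rate with time on treatment

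*SAP*

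**What the plan says.** Protocol 6.1.2 lists among the additional secondary objectives: "To compare transfusion requirements (platelet and red blood cell [RBC]; number of units transfused), infection rates, days spent hospitalized". SAP 3.1.2 repeats it. Protocol 12.5.2.2.4 and SAP 7.8.8 promise descriptive statistics by arm.

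The SAP treats the three named measures differently:

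- **Transfusions (SAP 7.8.8.1.1).** "The summary of on-treatment transfusion data will include the frequency of subjects with any on-treatment transfusions", then the frequency by type, "the total number of units per subject with each type of on-treatment transfusion", and the reasons. There is no rate per unit of time.
- **Infection (SAP 7.8.1.1).** Infection and bleeding come under this heading: "Additional TEAEs of interest indicative of clinical benefit are as follows". They are tabulated by preferred term, grade and seriousness. The counting rule in SAP 7.8.1 is: "Each subject will be counted only once within each SOC or PT". The result is a proportion of subjects.
- **Hospitalization (SAP 7.8.8.1.2).** "Hospitalizations for AE will be summarized, including number of events, total number of days hospitalized, the rate of events and days hospitalized per person-year". This is the only person-time denominator in either document, and the person-time is not defined.

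The window for the first two is set in SAP 6.3.5: "The on-treatment period starts on the date of the start of study treatment and ends 28 days after the end of study treatment". SAP section 4 makes its length depend on outcome: "Subjects should continue to receive therapy with AG-120 or placebo+azacitidine until death, disease relapse, disease progression", and other listed reasons.

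**The concern.** A total of units, or a proportion of subjects with an event, rises with time observed even when the underlying rate does not change. The design expects AG-120 to produce more remissions, longer remissions and longer survival, and each of these lengthens treatment. The arm that does better therefore gets more time in which to accrue transfusions, infections and bleeds. These tables are meant to show clinical benefit, and a true reduction per month of treatment could appear in them as no difference or as a small excess. The SAP already reports hospitalization per person-year and gives no reason for leaving the other measures without a time base.

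**Working it through.** **The plan's own figures first.** The documents give no numbers for transfusions or infections, so the inputs used below were checked against related stated figures.

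- OS power (SAP 6.2.1: 145 deaths, HR 0.71, 1-sided 2.5%): Φ(|ln 0.71| × √(145/4) − 1.960) = Φ(0.3425 × 6.021 − 1.960) = Φ(0.102) = 54.1%. The plan states 54%.
- Accrual (Protocol 12.12): 3 × 10 + 5 × 34 = 200.
- Deaths expected by month 52 with exponential survival and no dropout: 149. The plan states about 145.

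**Expected time on treatment by arm.** Simulated with the stated accrual and a cutoff at month 52.

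- Model A: treatment until death or cutoff, with median OS 10.4 vs 14.6 months.
- Model B: CR by 24 weeks in 20% vs 40%. Responders are treated until an EFS event (median 14.6 vs 19.2 months). Non-responders have an assumed mean of 2, 4, 6 or 8 months, the same in both arms. 28 days are added.

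**Effect on the summaries.** With a constant event rate (assumed):

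- ratio of units per subject = rate ratio × exposure ratio;
- break-even rate ratio = 1 / exposure ratio;
- probability of at least one event = 1 − E[exp(−rate × time)].

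The last column assumes an equal infection rate of 1 per person-year in both arms.

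| Model | Mean months, control vs AG-120 | Exposure ratio (= units ratio at equal rates) | Break-even rate ratio | Units ratio at true rate ratio 0.90 | % with ≥1 infection |
|---|---|---|---|---|---|
| A | 11.95 vs 14.64 | 1.23 | 0.82 | 1.10 | 52.8 vs 59.4 |
| B, 2 months | 5.39 vs 8.68 | 1.61 | 0.62 | 1.45 | 28.9 vs 38.9 |
| B, 4 months | 6.94 vs 9.84 | 1.42 | 0.71 | 1.28 | 36.7 vs 44.7 |
| B, 6 months | 8.37 vs 10.92 | 1.30 | 0.77 | 1.17 | 42.6 vs 49.1 |
| B, 8 months | 9.67 vs 11.88 | 1.23 | 0.81 | 1.11 | 47.1 vs 52.5 |

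Over assumed infection rates of 0.5 to 4 per person-year, the excess of subjects with an infection at equal rates is about 3 to 10 points. At 1 per person-year and a 10% lower rate on AG-120, that arm still shows more subjects with an infection in every model (for example 56.6% vs 52.8% in A).

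**Relaxing the constant rate.** Suppose instead an equal transfusion rate before remission, with responders transfused for 3 months and then not at all. The units ratio is (0.6 × n + 0.4 × 3) / (0.8 × n + 0.2 × 3), where n is the non-responder mean in months. It is 1.09 for n = 2, 0.95 for 4, 0.89 for 6 and 0.86 for 8. Dividing by the Model B exposure ratio for the same n gives a rough ratio of units per person-time: 1.09/1.61 = 0.68, 0.95/1.42 = 0.67, 0.89/1.30 = 0.68 and 0.86/1.23 = 0.70. Raw totals near parity would then sit beside a rate about 30% lower on AG-120. That lower rate comes wholly from transfusion-free time in remission, because the rates before remission were set equal.

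**The case against.** The strongest objection is to the constant rate. Much of the extra AG-120 time in Model B is time in remission, and CR requires RBC transfusion independence together with platelet and neutrophil recovery (Protocol 6.2.2 and Table 10). Protocol 9.8.2.2 places azacitidine cytopenias particularly in the first two cycles. Front-loaded transfusions shrink the distortion, and under the second illustration raw totals are near parity or favour AG-120. This stands. It also means that a crude person-time rate on its own would favour the longer-treated arm.

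A reader might infer that the raw totals are always biased against AG-120, or take the ratio of planned OS medians, 14.6/10.4 = 1.40, as the exposure ratio and expect 40% more units at equal rates. The documents support neither. Treatment also stops at relapse, progression or toxicity, follow-up is cut at about month 52, and nothing in the plan says that rates are constant.

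The wording of the objective gives the plan some cover. It names the number of units transfused, which is what SAP 7.8.8.1.1 reports, and these documents often use rate for a proportion, as in CR rate. Bleeding is not named in that objective; the SAP adds it as an indicator of benefit. These readings are fair, but units or proportions collected over unequal windows still need a common time base before the arms can be compared.

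Finally, SAP 7.4.1 tabulates duration of exposure by arm, and transfusion dates and units are listed by subject. A rate could be worked out later, but its denominator would then be chosen after unblinding.

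**Conclusion.** The point holds as a gap in the descriptive summaries. Without a time base, the transfusion, infection and bleeding tables combine event rate and treatment duration, and under the design assumptions duration is expected to be longer on AG-120. The comparison can hide a lower rate on AG-120 and, for a modest benefit, reverse it.

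Under constant rates, AG-120 would show more units per subject unless its true rate ratio fell below a break-even of 0.62 to 0.82. These sizes rest on the planned CR, EFS and OS assumptions holding, on assumed non-responder durations of 2 to 8 months, on assumed infection rates and on constancy. If events cluster early or stop after CR, the distortion is smaller, and for transfusions its direction is not established.

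These are additional secondary measures. Protocol 12.5 places them outside alpha control and no decision rule uses them, so the interpretation of benefit is affected and the primary claim is not.

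**What to change.** Keep the raw summaries and add to SAP 7.8.8.1.1 and 7.8.1.1, by arm:

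1. RBC units, platelet units, infection events and bleeding events per on-treatment person-year. Define person-time as the on-treatment period in SAP 6.3.5, ending at death or data cutoff if earlier, and use the same definition for the hospitalization rate in 7.8.8.1.2, which has none.
2. The same measures over a fixed common window, for example the first 24 weeks. This is needed beside the rate because, with front-loaded events, a crude rate alone favours the longer-treated arm.
3. A statement of whether the units summary covers all treated subjects or only those who received that type of transfusion. If only the latter, subjects who avoid transfusion drop out of the comparison.

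The cost is a few extra descriptive table rows. Transfusion dates and units, adverse event dates and dosing dates are already collected.
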